#### 6.1.1. COVID-19

Study LMDC was fully enrolled at the time the COVID-19 pandemic had impacted the countries participating in LMDC (March 1, 2020). The following summaries including treatment comparisons will be made to assess the impact of the pandemic on the study:

- Number of patients who discontinued the study early due to the pandemic

- Number of patients who used phone visits to replace site visits due to the pandemic
- Number of patients who used video visits to replace site visits due to the pandemic
- Number of patients who had out-of-window visit intervals due to the pandemic

All patients who are impacted by COVID as described above will have their iADRS data censored from that time forward and the DPM and MMRM will be assessed. In other words, patients' data after a temporary discontinuation of study drug because of COVID will be censored in order to assess if COVID impacted the DPM and MMRM analyses of iADRS.

## 6.2. Adjustments for Covariates

The repeated measures models will include the fixed, categorical effects of baseline score, pooled site, treatment, visit, treatment-by-visit interaction, baseline-by-visit interaction, concomitant AChEI and/or memantine use at baseline (yes/no), and age at baseline.

When an analysis of covariance (ANCOVA) model is used to analyze a continuous efficacy variable, the model will contain the main effects of treatment and appropriate baseline value included as a covariate. When an ANCOVA model is used to analyze a continuous safety variable, the model will contain the main effects of treatment, age, and appropriate baseline value included as a covariate.

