## 5. Study Design

### 5.1. Summary of Study Design

Study LMDC is a multicenter, randomized, double-blind, placebo-controlled, Phase 2 study of LY3303560 in patients with early symptomatic AD and low-to-medium cerebral tau burden. A combination of visual and quantitative assessments of tau PET is used to identify eligible patients:

- Visual assessment of AD+ (increased activity in posterior temporal regions only) AND  $1.10 < \text{SUVR} \leq 1.46$
- Visual assessment of AD++ (increased activity in temporal and parietal regions) AND  $\text{SUVR} \leq 1.46$

The maximum possible duration of the study is 121 weeks that includes a screening period of up to 8 weeks, a treatment period of 100 weeks, a 4-week post last dose assessment, and an immunogenicity and safety follow-up period of up to 13 weeks, following the last dose of the study drug at Week 100. Subjects who meet entry criteria will be randomized in a 1:1:1 ratio to one of the following treatments:

- **1400 mg LY3303560:** LY3303560 1400 mg IV infusion Q4W for 100 weeks (Visit 2 [Week 0] to Visit 27 [Week 100]).
- **5600 mg LY3303560:** LY3303560 5600 mg IV infusion Q4W for 100 weeks (Visit 2 [Week 0] to Visit 27 [Week 100]).
- **Placebo:** IV placebo infusion Q4W for 100 weeks (Visit 2 [Week 0] to Visit 27 [Week 100]).

The first safety review by a Data Monitoring Committee will be conducted after approximately 30 patients have received 3 doses and completed the 4 week assessment period ( i.e. just prior to their 4th dose). Enrolment will halt after these patients have received one dose of study treatment, however those patients already dosed will continue their allocated treatment. If any of these patients discontinue from study treatment for reasons other than safety, they may be replaced, upon discussion between the investigators and Lilly.

The primary hypothesis being tested is that LY3303560 administered for 100 weeks will result in a significant slowing in cognitive/functional decline compared with placebo as measured by the change from baseline to the end of the double-blind period (Week 104) on the integrated Alzheimer's Disease Rating Scale (iADRS), in subjects with early symptomatic AD (where early symptomatic AD refers to the combination of 2 stages: prodromal AD [mild cognitive impairment (MCI)-AD] and mild dementia due to AD; Alaka et al. 2015) who have low-to-medium tau burden.

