### 5.3. Method of Assignment to Treatment

Patients who meet all criteria for enrollment will be assigned a study (patient) number at Visit 1 and randomized to double-blind treatment at Visit 2. Patients will be randomized to LY3303560 or Placebo in a 1:1:1 ratio. Assignment to treatment groups will be determined by a computer-generated random sequence using an interactive web response system (IWRS). For the first, approximately, 30 patients, the IWRS will be programmed to guarantee balance between the arms for the first interim analysis for safety; this is referred to as the burn-in period. After the burn-in period, patient randomization will then follow the dynamic allocation (minimization) method of Pocock and Simon (1975) to balance the treatment arms using investigative site as a factor. This is to ensure balanced patient assignment between treatment arms within each site at the end of the study.

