## 6.11. Efficacy Analyses

### 6.11.1. Primary Outcome and Methodology

The primary objective of this study is to test the hypothesis that IV infusion of LY3303560 will slow the cognitive and/or functional decline of AD as measured by the composite measure iADRS compared with placebo in patients with early symptomatic AD. This will be assessed using a Disease Progression Model (DPM).

The iADRS at each scheduled visit (according to the SoA) during the treatment period will be the dependent variable. The DPM is as follows:

$$Y_{ij} = \gamma_i + e^{\theta T_i} \sum_{v=0}^j \alpha_v + \mathbf{x}'_i \boldsymbol{\beta} + \varepsilon_{ij}, i = 1, 2, \dots, k; j = 1, 2, \dots, l$$

where  $Y_{ij}$  denotes the clinical outcome at visit  $j$  for participant  $i$  and clinical outcome score at baseline (prior to treatment) is  $Y_{i0}$ .  $\gamma_i$  ( $i=1, 2, \dots, k$ ) represents the random participant effects.  $T_i$  denotes the treatment arm for participant  $i$ .  $T_i$  takes a value of 1 if a participant is randomized to the low dose, a value of 2 for high dose, and a value of 0 for placebo.  $e^{\theta T}$  is the disease progression ratio (DPR) for treatment  $T$  and  $e^{\theta T} = 1$  for placebo.  $e^{\theta 1}$  and  $e^{\theta 2}$  represent the DPR of the low dose and the high dose, respectively. Furthermore,  $\alpha_v$  is the change in mean cognitive score for placebo from visit  $v-1$  to  $v$ .  $\varepsilon_{ij}$  is the error term. Additional covariates  $\mathbf{x}_i$  will include pooled site ID, age, and baseline AChEI/memantine use (yes/no).

The DPM model assumes the treatment effect of LY3303560 is proportional to placebo over the course of the study. This proportionality assumption is similar to the assumption made in proportional hazards modeling of time to event data. The DPM includes generally diffuse priors on all parameters. The precision value for the prior distribution of all parameters is set to a small value; therefore, the prior distributions on all parameters have very little impact on the posterior distributions. No information or knowledge of the effect of LY3303560 from previous studies will be incorporated into the prior distributions, and the inference will be based on Study LMDC only. Diffuse priors will be used.

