### **6.11.3. Additional Exploratory Analyses of the Primary Outcome**

#### **6.11.3.1. Mixed Model Repeated Measures (MMRM)**

The change from baseline score on the iADRS at each scheduled postbaseline visit (according to the Schedule of Activities) during the treatment period will be the dependent variable. The model for the fixed effects will include the following terms: baseline score, pooled site, treatment, visit, treatment-by-visit interaction, baseline-by-visit interaction, concomitant AChEI and/or memantine use at baseline (yes/no), and age at baseline. Visit will be considered a categorical variable. The null hypothesis is that the contrast between the LY3303560 group versus placebo at the Visit 28, Week 104 (4 weeks after the final dose of LY3303560) equals zero. An unstructured covariance matrix will be used to model the within-subject variance-covariance errors. If the unstructured covariance structure matrix results in a lack of convergence, the following tests will be used in sequence: heterogeneous Toeplitz covariance structure, heterogeneous autoregressive covariance structure, heterogeneous compound symmetry covariance structure, and compound symmetry covariance structure. The Kenward-Roger approximation will be used to estimate the denominator degrees of freedom.

The primary time point for treatment comparison will be at Week 104. The treatment group contrast in least-squares mean change from baseline score on the iADRS scale and its associated p-value and 95% CI will be calculated for treatment comparisons of LY3303560 versus placebo using the MMRM model specified above.

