#### **6.11.3.5. Bayesian Analysis of Shared Control**

Sensitivity of comparative inference for slowing the cognitive and/or functional decline of AD based on the shared control may be accomplished via Bayesian mixture modeling.

Supplementing the iADRS analyses with placebo data from studies I5T-MC-AACG, I8D-MC-AZES, and H8A-MC-LZAX will be explored and potentially based on matching baseline tau PET scan results (Viele, 2014).

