## 6.14. Subgroup Analyses

To assess the effects of various demographic and baseline characteristics on treatment outcome, subgroup analyses for the primary endpoint, iADRS:

- APOE4 Carrier Status – Carrier defined as E2/E4, E3/E4, or E4/E4 genotype; No-Carrier defined as all other genotypes
- Disease status at baseline based on MMSE total score
  - MCI or mild AD (MCI: 27-30; mild AD: 20-26)
  - Grouped into thirds
- Tau burden at baseline based on eligibility tau PET SUVR
  - very low tau:  $SUVR < 1.10$ ; low tau:  $1.10 \leq SUVR < 1.23$ ; medium tau:  $1.23 \leq SUVR < 1.46$
  - Grouped into thirds

The primary outcome measure will be modeled using a DPM approach. This general model will include terms for baseline, treatment, pooled site, visit, concomitant AChEI/memantine use at baseline (yes/no), baseline age, treatment by visit, subgroup by treatment, subgroup by visit, and treatment by visit by subgroup. Redundant terms will be dropped from the model in those cases where the subgroup of interest is overlapping with this general model. In order to run these analyses, at least 20 patients are required in each strata-treatment combination.

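### Baseline tau PET SUVR is left out of the primary DPM and every whole-population iADRS model, forgoing possible precision and leaving chance tau imbalance unadjusted

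*SAP*

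**What the plan says.** The covariate lists agree with one another, and none of them contains tau.

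- **Primary DPM (6.11.1).** The additional covariates "will include pooled site ID, age, and baseline AChEI/memantine use (yes/no"). They enter as a constant shift in score level, beside a random participant effect.
- **Repeated-measures rule (6.2).** "The repeated measures models will include the fixed, categorical effects of baseline score, pooled site, treatment, visit, treatment-by-visit interaction, baseline-by-visit interaction", followed by AChEI/memantine use and age.
- **iADRS MMRM (6.11.3.1).** "baseline score, pooled site, treatment, visit, treatment-by-visit interaction, baseline-by-visit interaction, concomitant AChEI and/or memantine use at baseline (yes/no), and age at baseline". The spline model (6.11.3.2) keeps these covariates. The slope, completer and per-protocol analyses (6.11.3.6 to 6.11.3.8) also have no tau term, nor do the MMRMs of the other clinical scales (6.11.4).

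Tau appears elsewhere in the plan.

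- **Entry (5.1).** "A combination of visual and quantitative assessments of tau PET is used to identify eligible patients", and both entry routes set an SUVR limit.
- **External placebo data (6.11.3.5).** Their use is "potentially based on matching baseline tau PET scan results".
- **Subgroups (6.14).** "Tau burden at baseline based on eligibility tau PET SUVR", by fixed cut-offs and by thirds, in a model that includes "subgroup by treatment, subgroup by visit, and treatment by visit by subgroup".
- **Baseline table and PET outcome.** Tau burden is summarised by arm (6.8), and baseline SUVR is a covariate when PET is itself the outcome (6.12.1).

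After the burn-in period, allocation uses minimisation "to balance the treatment arms using investigative site as a factor" (5.3). Tau is not a balancing factor.

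**The concern.** Restricting entry by tau, considering tau as the basis for matching outside placebo patients, and splitting the primary endpoint by tau all suggest that the authors expect iADRS decline to vary with tau burden. If it does, two things follow. Variation in decline that a baseline value already on file could explain stays in the error of the Week 104 contrast and of the disease progression ratio (DPR). And because only site is balanced, the arms may differ in mean SUVR by chance. No whole-population iADRS analysis would then show how much of the estimated slowing reflects that difference.

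**Working it through.** **Inputs from the SAP.** Section 5.2 gives 360 patients, 30% dropout, a Week 104 variance of 436.85 (SD 20.9), placebo decline of 19.56, slowing of 33% and 50%, and a 4-point margin. With 1:1:1 allocation, 360/3 = 120 per arm and 120 × 0.7 = 84 completers. The front page gives about 225 patients, so 75 per arm is shown as well.

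**Input not in the SAP.** The partial correlation ρ between baseline SUVR and Week 104 iADRS change, given the other covariates, is an assumption. The values 0.2, 0.3 and 0.4 are shown; zero is also possible.

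**1. The plan's own figure.** Section 5.2 states more than 95% power from a simulation whose full covariance matrix is not given, so it cannot be reproduced exactly. A two-mean comparison at Week 104 with 50% slowing (9.78 points) has 95.2% power with 120 per arm and 85.8% with 84. The rule of at least 25% slowing with posterior probability at least 0.6 in either arm, by normal approximation without the onset delay, gives 97.6% and 95.3%. The stated power is plausible and needs no tau covariate.

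**2. Week 104 contrast.** Adjustment multiplies the residual variance by 1 − ρ².

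| ρ | variance cut | equivalent N = 360/(1 − ρ²) |
|---|---|---|
| 0 | 0% | 360 |
| 0.2 | 4% | 375 |
| 0.3 | 9% | 396 |
| 0.4 | 16% | 429 |

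On the power scale, if tau explains 10% of the variance, the 85.8% above becomes 89.2%. At 2% explained it becomes 86.5%.

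**3. Chance imbalance.** The SD of the error from this source is ρ × 20.9 × √(2/n). At ρ = 0.3, a 2-SD imbalance gives:

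- n = 120: 2 × 0.3 × 20.9 × √(2/120) = 1.6 points
- n = 75: 2 × 0.3 × 20.9 × √(2/75) = 2.05 points

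The standard error of the contrast at n = 120, before dropout, is 20.9 × √(2/120) = 2.7, so such a shift is 2ρ = 0.6 of a standard error. These figures use the full SD. After adjustment for baseline score, age and site the residual SD, and so the shift, would be smaller.

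**4. Form of the term in a progression model.** A random-intercept simulation had 84 per arm, no treatment effect, an assumed variance split, and tau explaining 10% of the change variance:

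| model | SD of estimated effect | correlation with tau imbalance |
|---|---|---|
| no tau | 3.19 | −0.34 |
| tau as a level shift | 3.16 | −0.32 |
| tau by time | 3.00 | −0.03 |

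A level term recovers almost nothing. Tau must act on decline.

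**5. Size in the DPM.** The figures are cuts in the variance of log DPR from a SUVR-by-visit term.

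| ρ | no treatment effect | 50% slowing |
|---|---|---|
| 0.2 | about 4–6% | about 0–1% |
| 0.3 | about 6–13% | about 2–4% |
| 0.4 | about 17–22% | about 9–14% |

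The 50% slowing runs had tau acting in proportion to decline and no dropout. They showed no bias from the centred term. Both columns depend on the assumed variance split. With 400 trials per setting under the null, a variance ratio carries simulation error of roughly 0.03. Read these as orders of magnitude.

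**The case against.** The strongest reply is that nothing here is an error. The covariate lists are consistent, and leaving a baseline variable out of a randomised comparison is legitimate. That stands, and it rules out the stronger reading that the primary result would be biased or its false-positive rate inflated. Chance imbalance is already part of the standard error. The DPM cutoffs are simulated from blinded data whose covariance already contains whatever variation tau causes.

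A second reply is that the SAP never calls tau prognostic. This is also correct. An entry window selects a population, subgroups look for effect modification, and the matching of external data is only tentative. Prognostic value is a fair inference from these uses taken together, but the plan does not state it. The SUVR ceiling of 1.46 narrows the tau range and may weaken any correlation.

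A third reply is that the plan partly covers the point. Section 6.8 would show an imbalance, and the tau subgroup DPM has subgroup-by-visit terms. But seeing an imbalance does not adjust for it, and the subgroup model uses categories, needs 20 patients per cell and does not give the overall estimate.

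A fourth reply concerns the primary model. A SUVR-by-visit term outside the DPR multiplier sits awkwardly with the assumption that treatment slows decline proportionally. The gain shrinks under a real effect, and cutoffs of 0.51 and 0.99928 are already fixed in 6.11.2. This is a good reason not to replace the primary DPM. It does not touch the MMRMs or a sensitivity analysis.

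**Conclusion.** The point holds as a modest improvement in efficiency and robustness, not as a flaw in validity. Baseline SUVR is available for all eligible patients, is not balanced by the allocation, and is absent from the primary DPM and from every whole-population iADRS model. For the Week 104 contrast the forgone precision is 4%, 9% or 16% of the variance at partial correlations of 0.2, 0.3 or 0.4, and nothing at zero. For the DPM it is similar under the null and smaller under a real effect. All of this rests on a correlation that the SAP does not give.

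A reader might also infer that the power claim of more than 95% fails without tau, or that the primary DPM must be respecified. Neither follows. The power claim does not rely on a tau covariate, and the gain in the DPM is too uncertain to justify reopening cutoffs that are already set.

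**What to change.** - **Repeated-measures models (6.2, 6.11.3.1, 6.11.4).** Add baseline eligibility SUVR and SUVR-by-visit for iADRS and the other clinical scales. State that SUVR is continuous, because the opening of 6.2 describes the listed effects as categorical.
- **Primary DPM (6.11.1, 6.11.2).** Leave the model and its cutoffs as they are.
- **Sensitivity analysis.** Before unblinding, prespecify a DPM with centred SUVR-by-visit as a visit-specific term, not as a constant in x_i'β. Report its DPR beside the primary one. The 0.51 and 0.99928 cutoffs were derived for the model without tau, so they should not be read as calibrated tests for this one.

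The cost is a few extra model parameters, one extra analysis and SAP wording. No new data are needed.

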#### **6.11.3.6. Slope Analyses**

Slopes of the iADRS will be assessed using an MMRM analysis. The change from baseline score at each post-baseline visit during the treatment period will be the dependent variable. The model will include the fixed, categorical effects of treatment, concomitant AChEI or memantine use at baseline (yes/no), pooled site, and continuous effects of baseline score, time, time-by-treatment interaction, and age at baseline. Time will be assumed to be a continuous variable calculated as number of days between baseline and each postbaseline visit (ie, [visit-baseline]+1) during the treatment period. The actual visit dates will be used to calculate number of days (time). The null hypothesis is that the contrasts of slopes of LY3303560 dose groups versus placebo equal zero.

A quadratic slopes model will also be fitted to these same scales. The quadratic model will include the linear component of time (TIME) and a quadratic component of time (TIME\*TIME), the linear component of time and treatment interaction (TIME\*TREATMENT) and quadratic component of time and treatment interaction (TIME\*TIME\*TREATMENT).

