#### **6.11.3.7. Completer Analyses**

The primary efficacy outcome, iADRS, from the dataset of those patients who remained in the study and on treatment through Week 104 (“completers”) will be analyzed using an ANCOVA. The change from baseline at Week 104 will be the dependent variable. The model will include the fixed, categorical effects of treatment, concomitant AChEI use at baseline (yes/no), pooled site, and the continuous effects of baseline iADRS score and age at baseline. The null hypothesis is that the differences in least-squares means between the LY3303560 dose groups versus placebo at Week 104 equal zero.

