## **6.12. Bioanalytical and Pharmacokinetic/Pharmacodynamic Methods**

### **6.12.1. Analysis of flortaucipir PET**

To evaluate the change from baseline in tau imaging parameters, an MMRM analysis will be used to compare change from baseline in SUVR at 104 weeks in the Evaluable Efficacy dataset. The model will include the fixed, categorical effects of treatment, visit, and treatment-by-visit interaction, as well as continuous effects of baseline SUVR and age at baseline. Visit will be considered a categorical variable with values equal to the visit numbers at which tau imaging is assessed. The null hypothesis is that the difference in LSM between the LY3303560 dose groups and placebo equals zero.

To assess the relationship of biomarker with cognition and function with treatment, Spearman's rank correlation coefficient will be obtained on change from baseline to Week 104 for the composite summary standard uptake value ratio (SUVR) normalized to bimodal white matter and with change from baseline to Week 104 for iADRS, ADAS-Cog13, ADCS-ADL, MMSE, and CDR-SB. Correlation analyses will be conducted using only patients who have the clinical outcome and SUVR result at Week 104 and include patients from all 3 dose groups.

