### **6.12.2. Analysis of NfL**

To evaluate the change from baseline in neurofilament light chain (NfL) concentrations, an MMRM analysis will be used to compare change from baseline between treatments up to 104 weeks of treatment in the Evaluable Efficacy dataset. All NfL values will be log transformed

prior to calculating baseline and change values. The model will include the fixed, categorical effects of treatment, visit, sex, and treatment-by-visit interaction, as well as continuous effects of log baseline, age, and log baseline-by-treatment interaction. Visit will be considered a categorical variable with values equal to the visit numbers at which NfL is assessed. The null hypothesis is that the difference in LSM between the LY3303560 dose groups and placebo equals zero.

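### SAP section 6.2 types baseline score, baseline-by-visit and age as categorical, against the SAP's own slope and biomarker models; for the clinical-scale MMRMs it is the only text that types them

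*SAP*

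**What the plan says.** Section 6.2 sets the general rule: the repeated measures models include "fixed, categorical effects of baseline score, pooled site, treatment, visit". The list then continues with treatment-by-visit, baseline-by-visit, AChEI/memantine use and age. One adjective, categorical, covers every item, and no grouping of baseline score or age is defined.

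The iADRS MMRM (6.11.3.1) gives the same terms without that adjective: "The model for the fixed effects will include the following terms: baseline score, pooled site, treatment, visit, treatment-by-visit interaction, baseline-by-visit interaction". It then types one of them: "Visit will be considered a categorical variable". Sections 6.11.4 (other clinical scales) and 6.17.1.1 (CBB and DCTClock) repeat the list and type neither baseline nor age. The spline model (6.11.3.2) keeps the same covariates, and the randomization test (6.11.3.3) reuses the MMRM statistic.

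Where the SAP does separate the two kinds of effect, it does the opposite of 6.2:

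- The slope model (6.11.3.6), which the SAP calls an MMRM, has "continuous effects of baseline score, time, time-by-treatment interaction, and age at baseline".
- The flortaucipir MMRM (6.12.1) has its categorical terms "as well as continuous effects of baseline SUVR and age at baseline".
- The NfL MMRM (6.12.2) has "continuous effects of log baseline, age, and log baseline-by-treatment interaction". The plasma tau (6.12.3) and vMRI (6.12.4) models follow the same pattern.
- The completer ANCOVA (6.11.3.7) has "the continuous effects of baseline iADRS score and age at baseline".

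**The concern.** A SAP should fix the model so that two competent programmers fit the same one. Here, one who follows 6.2 enters each distinct baseline score as a class and crosses it with visit. One who follows the pattern of the other sections fits a slope per visit. The two models share a term list but differ greatly in parameters, degrees of freedom and precision. The difference carries into every analysis that reuses the iADRS MMRM.

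**Working it through.** The SAP gives no figure for this point, so the check counts parameters under both codings and then tests estimability and precision on synthetic patients.

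**Inputs from the SAP.** N is 360 (5.2) or approximately 225 (title page); both were used. Dropout is 30% (5.2) and allocation 1:1:1 (5.3). The ADAS-Cog13 maximum is 85 and the ADCS-iADL maximum 59 (6.3.2), so iADRS runs from 0 to 85 + 59 = 144, or 145 possible integer values.

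**Assumptions, not in the SAP.** Baseline iADRS mean 105, SD 10 to 15; age mean 75, SD 5.5, range 60 to 85; S = 20 or 50 pooled sites; J = 4, 5 or 8 post-baseline visits.

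**Parameter count.** Let L be the number of observed baseline levels and A the number of observed ages. Intercept, treatment, visit and treatment-by-visit take 3J, sites S − 1 and AChEI/memantine use 1.

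- Continuous: baseline and baseline-by-visit take J, age takes 1. Total 4J + S + 1.
- Categorical: baseline and baseline-by-visit take (L − 1)J, age takes A − 1. Total J(L + 2) + A + S − 1, less any empty cells.

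Example, N = 360, SD 10, S = 20, J = 4, giving L = 48 and A = 25:

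- Continuous: 16 + 20 + 1 = 37.
- Categorical: 4 × 50 + 25 + 20 − 1 = 244. The computed rank was 239, the shortfall coming from empty cells.

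Over 16 settings the fixed-effects rank was 37 to 83 with continuous covariates and 222 to 602 with categorical ones (L = 44 to 66, A = 24 or 25).

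**Residual degrees of freedom at Week 104.** In the same example 246 patients are observed at Week 104 and 46 of the 48 baseline levels are occupied.

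- Continuous: 246 − (1 + 2 + 1 + 1 + 19 + 1) = 246 − 25 = 221.
- Categorical: 246 − (1 + 2 + 45 + 24 + 19 + 1) = 246 − 92 = 154.

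**Results over the 16 settings.** The standard error is that of the treatment difference in the Week 104 cross-section, with the residual variance held equal under both codings.

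| | N = 225 | N = 360 |
|---|---|---|
| Residual df, continuous | 114 to 140 | 191 to 221 |
| Residual df, categorical | 37 to 79 | 108 to 154 |
| Rise in standard error | 27 to 67% | 15 to 36% |

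The ends of the range are 0.1895 / 0.1648 = 1.15 (N = 360, SD 10, 20 sites) and 0.3783 / 0.2271 = 1.67 (N = 225, SD 15, 50 sites).

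A separate cross-sectional check on 320 simulated datasets, with its own assumed baseline spread and site counts, gave a rise of about 19 to 86%. Residual df fell from about 104–132 to 29–71 at N = 225, and from 196–226 to 111–158 at N = 360. Together the checks span roughly 15 to 85%.

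**Estimability.** The Week 104 treatment difference was estimable in all 16 settings, in 160 further repeats (SD 12, five visits) and in the 320 datasets. The arm least-squares mean at Week 104, averaged equally over levels, was estimable in none of the 16 settings. In the repeats it was estimable in 0% at N = 225 and 2.5% at N = 360. The cause is baseline levels with no patient left at Week 104 (2 to 4 in the 16 settings). Their terms cancel in a treatment difference but not in an arm mean.

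**The case against.** The best defence is that the intent is plain. Every model that types baseline makes it continuous. Section 6.11.3.1 drops the adjective and then declares visit categorical, which would be redundant if every listed term already were. The SAP nowhere says that 6.2 overrides a section's own term list, and a programmer would probably use continuous terms. This stands as evidence of a drafting slip and keeps the severity low. It does not remove the contradiction, and it leaves 6.2 as the only text that types these covariates for the clinical-scale and CBB/DCTClock models. The completer analysis is an ANCOVA, so it shows intent rather than a direct conflict with a rule about repeated measures.

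A reader might infer more than the documents support:

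- That the MMRM could not be estimated. For iADRS the treatment difference survived in every simulated case; precision and the arm means suffer.
- That the model is over-saturated, by setting an assumed 50 to 80 levels × 8 visits = 400 to 640 parameters against 360 patients. Each patient contributes several visits: 360 × 8 = 2,880 observations before dropout. Within one visit the comparison is 50 to 80 levels against up to 360 patients.
- That all repeated measures models are affected. The slope and biomarker models set their own terms.
- That the primary result is at risk. The primary and gated tests use the disease progression model, whose covariates are set in 6.11.1. The MMRM behind its thresholds (6.11.2) lists its own adjustments and has no baseline-by-visit term.

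**Conclusion.** Wrong as written, low severity. Section 6.2 contradicts sections 6.11.3.6 and 6.12.1 to 6.12.4. The ambiguity is live in 6.11.3.1, 6.11.4 and 6.17.1.1, and in the spline and randomization-test analyses that build on the iADRS MMRM. Literal use would leave the Week 104 iADRS contrast estimable, with a standard error roughly 15 to 85% larger, far fewer residual degrees of freedom, and arm least-squares means that are generally not estimable.

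These sizes rest on the assumed baseline SD, age spread, site count and visit count. They come from a Week 104 cross-section rather than a full MMRM fit, so they indicate scale only. For CBB and DCTClock the SAP does not say how finely baseline is scored. If values were nearly unique to each patient, categorical coding could cost the contrast itself, but that is conditional and was not tested.

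**What to change.** Reword 6.2 so that treatment, visit, treatment-by-visit, pooled site and AChEI/memantine use at baseline are categorical, and baseline score, baseline-by-visit (continuous baseline crossed with categorical visit) and age are continuous. Add a cross-reference to 6.2 in sections 6.11.3.1, 6.11.4 and 6.17.1.1; the spline and randomization-test sections then inherit it. The cost is a few lines of SAP text. Data collection, sample size and the primary analysis do not change.
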